## 1 Introduction

[REDACTED]

[REDACTED]

[REDACTED]

(RANITLES), and other substrates.

[REDACTED]

stimulating excretion (AED).

[REDACTED]

[REDACTED]

[REDACTED]

[REDACTED]

[REDACTED]

[REDACTED]

[REDACTED]

[REDACTED]

[REDACTED]

[REDACTED]

[REDACTED]

[REDACTED]

[REDACTED]

[REDACTED]

[REDACTED]

[REDACTED]

[REDACTED]

[REDACTED]

[REDACTED]

[REDACTED]

[REDACTED]

[REDACTED]

[REDACTED]

[REDACTED] [REDACTED]

[REDACTED]

[REDACTED]

[REDACTED]

[REDACTED]

[REDACTED]

[REDACTED]

[REDACTED]

[REDACTED]

[REDACTED]

[REDACTED]

[REDACTED]

[REDACTED]

[REDACTED]

[REDACTED]

[REDACTED]

[REDACTED]

[REDACTED]

[REDACTED]

[REDACTED]

[REDACTED]

[REDACTED]

[REDACTED]

[REDACTED]

[REDACTED]

[REDACTED]

[REDACTED]

[REDACTED]

[REDACTED]  
[REDACTED]  
[REDACTED]  
[REDACTED]

[REDACTED]  
[REDACTED]  
[REDACTED]  
[REDACTED]

[REDACTED]  
[REDACTED]  
[REDACTED]

[REDACTED] [REDACTED]

[REDACTED] [REDACTED]

[REDACTED]  
[REDACTED]  
[REDACTED]  
[REDACTED]

[REDACTED]  
[REDACTED]  
[REDACTED]

[REDACTED]  
[REDACTED]  
[REDACTED]

[REDACTED] [REDACTED]

[REDACTED]  
[REDACTED]  
[REDACTED]  
[REDACTED]

[REDACTED]  
[REDACTED]  
[REDACTED]

[REDACTED]  
[REDACTED]  
[REDACTED]

[REDACTED]  
[REDACTED]  
[REDACTED]

[REDACTED]  
[REDACTED]  
[REDACTED]  
[REDACTED]

[REDACTED]

[REDACTED]  
[REDACTED]  
[REDACTED]

[REDACTED]  
[REDACTED]  
[REDACTED]  
[REDACTED]  
[REDACTED]  
[REDACTED]  
[REDACTED]  
[REDACTED]

[REDACTED]  
[REDACTED]  
[REDACTED]  
[REDACTED]  
[REDACTED]

[REDACTED] [REDACTED]  
[REDACTED]  
[REDACTED]

[REDACTED]  
[REDACTED]  
[REDACTED]  
[REDACTED]  
[REDACTED]  
[REDACTED]  
[REDACTED]

[REDACTED]  
[REDACTED]  
[REDACTED]

[REDACTED]

[REDACTED] [REDACTED]  
[REDACTED]  
[REDACTED]  
[REDACTED]  
[REDACTED]  
[REDACTED]

[REDACTED]  
[REDACTED]  
[REDACTED]  
[REDACTED]

[REDACTED]  
[REDACTED]  
[REDACTED]  
[REDACTED]  
[REDACTED]

### 1.3 Rationale for Phase 2a Study MT-0814/2-01

Age-related macular degeneration is the leading cause of blindness among adults in North America and Europe, and it is the fourth-leading cause of visual disorders in Japan. Moreover, the prevalence of AMD has increased in recent years, and its incidence is expected to increase further due the continued aging of the world population. In exudative (wet) AMD, CNV formation is induced by the secretion of vascular endothelial growth factor (VEGF), leading to a rapid decrease in visual acuity due to retinal edema and/or bleeding.

The current standard of care for patients with exudative AMD is the administration of anti-VEGF agents (aflibercept or ranibizumab) via an intravitreal injection every 4 to 8 weeks. Treatment with anti-VEGFs has been demonstrated to benefit patients with AMD by maintaining or even improving visual acuity. However, lifetime dosing of anti-VEGF every 1 to 2 months exposes patients to the risk of acquiring infectious diseases from the intravitreal injection procedure. Additionally, the intravitreal injection procedure itself places a severe burden on patients, caregivers, and ophthalmologists.

[REDACTED]

[REDACTED]

[REDACTED]

[REDACTED]

[REDACTED]

[REDACTED]

[REDACTED]

[REDACTED]

[REDACTED]

[REDACTED]

[REDACTED]

[REDACTED]

[REDACTED]

[REDACTED]

As MT-0814 is an investigational drug with a limited safety profile in humans, all subjects receiving MT-0814 will be closely monitored until sufficient exposure in humans is obtained to determine the clinical safety of MT-0814.

## 1.4 Risk-Benefit Assessment

Any potential risks associated with MT-0814 are considered low, based on results obtained from animal model repeat-dose toxicity studies, as the no observed adverse effect level for MT-0814 for both male and female animals [REDACTED]

[REDACTED]

[REDACTED] Please refer

to the Investigator's Brochure for detailed information concerning the available nonclinical and clinical information of MT-0814.

## **2 Study Objectives**

### **2.1 Primary Objectives**

The primary objective of this study is to assess the safety, tolerability, efficacy, and PK of [REDACTED] MT-0814 administration versus placebo in subjects with AMD.

[figure not shown]
### 3 Investigational Plan

#### 3.1 Study Design

This is a double-masked, randomized, multicenter, placebo-controlled, parallel-group study in adult subjects with exudative AMD. Subjects will be randomly assigned in a 3:3:1 allocation ratio to receive MT-0814 [REDACTED], MT-0814 [REDACTED], or placebo [REDACTED] for 12 weeks, [REDACTED] followed by a 4-week follow-up period. Randomization will be stratified by the BCVA score category (BCVA scores of  $\leq 55$ , 56 to 70, or  $\geq 71$ ) observed for the subject's study eye on Day 1 (Baseline).

This study is planned to last up to 18 weeks (with 18 study visits), including a screening/washout period of  $\leq 14$  days ( $\leq 2$  weeks), a 12-week treatment period, and a 4-week follow-up period in which study drug will not be administered (Figure 3–1).

**Figure 3–1 Study Design: Study Periods and Visit Schedule**

Abbreviations: [REDACTED] BSL = Baseline; EOS = end of study; EOT = end of treatment; RAN = randomization; SOT = start of treatment.

\* Baseline assessments for fluorescein angiography, indocyanine green angiography, and color fundus photography will be collected at Screening (Visit 1) instead of Visit 2.

For subjects who used prohibited concomitant medications within 14 days prior to the planned randomization date, a washout period will be required prior to the first dose of study drug. The duration of this washout must be a minimum of 14 days for any prohibited ocular, nasal, and systemic medications (defined as those delivered by injection, oral, or transdermal methods) prior to the planned randomization date.

Approximately 35 subjects will be enrolled in the study. Once the Screening visit laboratory test results are confirmed, subjects who still meet all inclusion criteria and none of the exclusion criteria will be randomly assigned in a 3:3:1 ratio to receive one of the following treatment regimens:

1. MT-0814 [REDACTED] for 12 weeks (N=15)
2. MT-0814 [REDACTED] for 12 weeks (N=15)
3. Placebo [REDACTED] for 12 weeks (N=5)

[REDACTED]  
[REDACTED]  
[REDACTED]  
[REDACTED] Following training and under supervision, subjects will receive the first dose of study drug at the study site on Day 1 (Week 0). If a subject withdraws prematurely from the study before the completion of the treatment period (that is, before the Week 12 visit), a final visit must be scheduled for End of Study (EOS) assessments.

Efficacy, safety, and plasma concentration assessments will be performed as presented in the schedule of events (SOE) (Table 13–1); the plasma concentration sample collection schedule is presented in Table 13–2. Efficacy, safety, and plasma concentration measures are listed below.

- The primary efficacy measure is the assessment of change (from Baseline) in BCVA (measured by the Early Treatment of Diabetic Retinopathy Study [ETDRS]) at Week 12.
- The key secondary efficacy measure is the assessment of change (from Baseline) in the CSFT at Week 12.
- Additional efficacy/safety measures include assessment of the changes observed from Baseline at each visit for the following:

- Best-corrected visual acuity
- Central subfield thickness
- Optical coherence tomography (OCT) parameters
- Total lesion area (as measured by fluorescein angiography [FA], indocyanine green angiography [ICGA], and color fundus photography [CFP])
- Choroidal neovascularization area (as measured by FA, ICGA, and CFP)
- Leakage area (as measured by FA, ICGA, and CFP)
- Regression of polypoidal choroidal vasculopathy (PCV)
- Proportions of subjects requiring anti-VEGF rescue therapy
- Proportions of subjects who achieve dry retina (defined as an absence of visible intraretinal cystoid edema or subretinal fluid on OCT scan) at Weeks 4, 8, 12 (EOT), and 16 (EOS).
- Duration from start of treatment (SOT) to the time that anti-VEGF rescue therapy is initiated.
- Other safety measures include monitoring of AEs, ophthalmological assessments (visual acuity, FA/ICGA, CFP, slit-lamp biomicroscopy examinations, and measurement of intraocular pressure [IOP]), physical examination findings, vital sign measurements, ECG findings, clinical laboratory tests, and monitoring of concomitant medications.
- Predose and 2-hour postdose plasma concentrations of MT-0814 and its metabolites M5 and M6 on Days 1, 29, 57, and 85 of the study.

### 3.1.1 Rationale for Study Design

This Phase 2a study has a double-masked, randomized, multicenter, placebo-controlled, parallel-group design. The study will evaluate the safety, tolerability, efficacy, and PK of [REDACTED] MT-0814 administration for the treatment of subjects with AMD. [REDACTED]

[REDACTED] given this fact, and given that this is a small, proof-of-concept study to detect whether MT-0814 is effective against the signs and symptoms of AMD, it is considered appropriate to compare the study

drug against a placebo. Subjects who participate in this study will be examined on a weekly basis, and rescue therapy (via anti-VEGF injection; refer to Section 4.2.3 for details) will be provided in the event that further disease-related deterioration is observed.

[REDACTED]

## 4 Subject Selection and Withdrawal Criteria

### 4.1 Selection of Study Population

Approximately 35 subjects are planned to be enrolled at approximately 15 sites in the United States (US). Subjects will be assigned to study treatment only if they meet all of the inclusion criteria and none of the exclusion criteria.

Deviations from the inclusion and exclusion criteria are not allowed because they can potentially jeopardize the scientific integrity of the study, regulatory acceptability, or subject safety. Therefore, adherence to the criteria as specified in the protocol is essential.

Ocular inclusion and exclusion criteria must all be met in the same eye for at least one of the subject's eyes — that eye will be the “study eye.” If both eyes meet all inclusion and exclusion criteria, the eye with the lower ETDRS score (that is, the eye in which fewer letters are correctly identified) at Screening will be selected as the study eye. If both eyes meet all entry criteria and have identical ETDRS scores at Screening, selection of the study eye will be at the investigator's discretion.

#### 4.1.1 Inclusion Criteria

Each subject must meet all of the following criteria to be enrolled in this study:

1. Is capable of understanding the written informed consent form (ICF), provides signed and witnessed written ICF, and agrees to comply with protocol requirements, including all required study visits.
2. Is a male or female 50 years of age or older.
3. Has active CNV (classic and/or occult), either subfoveal or juxtafoveal (<200  $\mu\text{m}$  from central fovea), associated with AMD, as evidenced on FA and/or ICGA at Screening and as assessed by a single central reading facility.
4. Has a total CNV area that is  $\geq 50\%$  of the total lesion area in the study eye at Screening as assessed by a single central reading facility.
5. Has an ETDRS BCVA score of 24 to 78 letters for the study eye at Screening and on Day 1.
6. Has a total lesion area <30.5  $\text{mm}^2$  in the study eye at Screening as assessed by a single central reading facility.
7. Has retinal/subretinal fluid in the study eye at Screening (detected by OCT scan) as assessed by a single central reading facility.
8. Has a clear optic media in the study eye that is capable of producing high-quality fundus images.

- [REDACTED]
10. If the subject is a female (either a female of childbearing potential or postmenopausal; both defined below), she must have a negative serum pregnancy test result at Screening (Visit 1). Additionally, female subjects who are premenopausal or have been postmenopausal for <1 year must have a negative urine pregnancy dipstick test result on Day 1 before being randomly assigned to study treatment. Females of childbearing potential must also agree to use effective contraception throughout the study.

A female of childbearing potential is defined as the following:

- Has experienced menarche and who has not undergone successful surgical sterilization (hysterectomy, bilateral tubal ligation, or bilateral oophorectomy) or is not postmenopausal. Women who are already using oral contraceptives, other hormonal contraceptives (vaginal products, skin patches, or implanted or injectable products), or mechanical products such as an intrauterine device or barrier methods (diaphragm, condoms, spermicides) to prevent pregnancy, or are practicing abstinence or who have a partner that is sterile (eg, vasectomy) should be considered to be of childbearing potential.

A postmenopausal female is defined as the following:

- Has had amenorrhea  $\geq 12$  consecutive months without another cause and a documented serum follicle-stimulating hormone level  $>35$  mIU/mL
- Has had irregular menstrual periods and a documented serum follicle-stimulating hormone level  $>35$  mIU/mL, or
- Has been on hormone replacement therapy

**Note:** If a female subject has a positive pregnancy test result (serum and/or urine dipstick) but the investigator suspects that the result is a false-positive, the female subject can participate in the study at the investigator's discretion.

11. If the subject is a male, he must agree to use an acceptable form of contraception (eg, a condom plus spermicide) and must agree to refrain from sperm donation throughout the study.
12. Is otherwise healthy, as determined by physical examination findings at Screening and Day 1.
13. Has a negative urine drug test result at Screening and Day 1.
  - If the investigator has medical evidence to support that the positive urine drug test result is due to a prescribed concomitant medication and not due to drug abuse, an exception can be granted to enroll a subject with a positive urine drug test. The site must appropriately document the decision for this specific scenario in the source documents and electronic case report form (eCRF).

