		
Change — The term “color funduscopy” was changed to “color fundus photography.”
 
Rationale — Added per the recommendation of the study’s coordinating investigator, [REDACTED]
 
7. Inclusion Criterion 10 and Schedules of Study Events (Table 13–1; Footnote #i)
 
Change — A statement of note was added that will allow female subjects with positive pregnancy test results to participate in the study if the investigator suspects the result to be a false-positive.
 
Rationale — Previous experience with studies involving elderly female subjects has demonstrated the occasional occurrence of false-positive pregnancy results in postmenopausal women.
 
8. Ocular Exclusion Criterion 16
 
Change — The criterion that excludes subjects who had previously received sub-Tenon injections of corticosteroid therapy into the study eye was revised from “within 12 months prior to Day 1” to “within 90 days prior to Day 1.”
 
Rationale — Revised per the recommendation of the study’s coordinating investigator, [REDACTED]
 
9. Missed Doses (Section 5.5.2)
 
Change — The last sentence of this section (“If a dose is considered missed, it should be marked in the diary as missed.”) was deleted.
 
Rationale — Technical oversight.
 
10. Recording of Prior and Concomitant Medications and Procedures (Section 5.8.1)
 
Change — The section was revised to include “and procedures” to both the section heading and the text.
 
Rationale — Typographical error.

		
11. Ophthalmological Assessments (Section 6.2.1)
 
Change — The section was revised to indicate that both slit-lamp biomicroscopy and slit-lamp examination will evaluate the condition of the eyelids, conjunctiva, anterior chamber, cornea, and lens of the eyes.
 
Rationale — Typographical error.
 
12. Clinical Laboratory Tests (Section 6.2.3): Serum Chemistry
 
Change — The list of serum chemistry parameters was revised to include “total cholesterol” and “C-reactive protein.”

Version Number	Approval Date	Summary of Changes

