### 6.2.3 Clinical Laboratory Tests

Clinical laboratory tests will be performed at the visits indicated in the SOE (Table 13–1). After Screening, all visits that include laboratory tests must occur after an 8-hour fast. Sample collection (blood, urine) should be performed before FA and ICGA are performed. Sample collection, processing, and shipping should be performed according to the local laboratory requirements.

Routine laboratory tests will be evaluated by a central laboratory and will include the following:

- **Hematology**: hemoglobin, hematocrit, red blood cell count, white blood cell count with differential, mean corpuscular volume, mean corpuscular hemoglobin, mean corpuscular hemoglobin concentration, and absolute platelet count.

- **Serum chemistry:** total protein, sodium, potassium, calcium, chloride, inorganic phosphate, albumin, fasting blood glucose\*, glycated hemoglobin, total cholesterol, high-density lipoprotein and low-density lipoprotein† cholesterol, follicle-stimulating hormone, human chorionic gonadotropin (β-subunit), triglycerides, blood urea nitrogen, creatinine, uric acid, bilirubin (total and direct), alkaline phosphatase, aspartate aminotransferase, C-reactive protein, alanine aminotransferase, γ-glutamyltransferase, lactate dehydrogenase, and creatine kinase.
- **Urinalysis:** pH, glucose, ketones, specific gravity, nitrite, protein, bilirubin, urobilinogen, and blood. Microscopic urinalysis will be performed if urinalysis results are abnormal.

\*Fasting at Screening is not required; therefore, glucose testing at Screening may be fasting or nonfasting. All subsequent laboratory tests should be performed after an 8-hour fast (see SOE, Table 13–1).

†Low-density lipoprotein will be directly measured (eg, beta-quantification [ultracentrifugation]) if a subject's triglyceride level is  $\geq 400$  mg/dL.

**Serum pregnancy test:** Serum pregnancy testing will be performed for all females at Screening (Visit 1) and the EOS visit.

**Urine dipstick pregnancy test:** On Day 1, a urine pregnancy dipstick test will be performed for all females who are either premenopausal or have been postmenopausal for <1 year to confirm their eligibility for assignment to study treatment.

**Urine drug test:** A screen for drugs of abuse will be performed at Screening and Day 1 according to the local laboratory standard practices.

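### The Note to inclusion criterion 10 lets a positive pregnancy test be overridden on investigator suspicion alone in any woman, which is wider than its stated reason and less demanding than the parallel exception in criterion 13

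*Combined protocol and SAP*

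**What the plan says.** Criterion 10 in Section 4.1.1 sets two test requirements. For every female subject, "she must have a negative serum pregnancy test result at Screening (Visit 1". In addition, "female subjects who are premenopausal or have been postmenopausal for <1 year must have a negative urine pregnancy dipstick test result on Day 1", before randomisation. Section 6.2.3 and Table 13-1 give the dipstick to the same restricted group.

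The Note at the end of criterion 10 begins "If a female subject has a positive pregnancy test result (serum and/or urine dipstick" and continues "but the investigator suspects that the result is a false-positive, the female subject can participate in the study", at the investigator's discretion. Footnote i of Table 13-1 carries the same Note with the same scope. Neither place mentions menopausal status, supporting evidence or a record of the decision.

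The reason for the Note is given in the amendment history (Amendment 1, item 7): earlier studies in elderly women had occasionally seen "false-positive pregnancy results in postmenopausal women".

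Criterion 13, in the same section, has an exception of the same kind for a positive urine drug test. It opens "If the investigator has medical evidence to support that the positive urine drug test result is due to a prescribed concomitant medication" and rather than drug abuse, and it obliges the site to document the decision in the source documents and the eCRF.

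**The concern.** A pregnancy test at entry exists to stop a pregnant woman from being given study drug. The Note allows a positive result to be set aside because the investigator suspects it is wrong, without saying what the suspicion must rest on. It applies equally to a woman many years past menopause, in whom a false positive is the likely explanation, and to a premenopausal woman, in whom a true positive is a real possibility.

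What is at stake is subject safety and the ability to audit the decision. Section 1.3 acknowledges that human safety data on MT-0814 are limited. Section 4.2.1 gives pregnancy as an example of a reason for ending participation, and Section 6.3 requires any pregnancy during the study to be reported and followed to its outcome. Entry after one or two positive tests, on suspicion alone and with no recorded basis, fits poorly with those provisions.

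**Working it through.** No arithmetic applies. The point uses no rate, effect size, standard deviation or sample size, and the plan gives no figure to reproduce. The check sets the relevant texts side by side.

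1. **Which women does the Note cover?** Its subject is a female subject, without qualification. Criterion 10 itself separates women of childbearing potential from postmenopausal women and defines both, so a restriction could have been stated in the protocol's own terms. None is.

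2. **Which tests does it cover?** Serum, dipstick or both. The dipstick is given only to women who are premenopausal or less than one year postmenopausal. For a woman longer past menopause, the mention of the dipstick has no application. Recently postmenopausal women account for part of the dipstick group, but premenopausal women are in it too, and unless surgically sterilised they are of childbearing potential under the criterion's definition. The Note therefore reaches women who could be pregnant.

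3. **How does that compare with its stated reason?** The Amendment 1 rationale names postmenopausal women only. The operative text is wider than the problem it was written to solve.

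4. **What does it take to use each exception?**

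| | Criterion 10 Note (pregnancy test) | Criterion 13 exception (drug test) |
|---|---|---|
| Basis | Investigator suspects a false positive | Medical evidence that a prescribed medication explains the result |
| Decision | Investigator's discretion | Exception can be granted |
| Record | None stated | Source documents and eCRF |

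5. **What would catch a mistaken override?** The pregnancy tests named as such are serum at Screening, the Day 1 dipstick in the restricted group, and serum at the end-of-study visit. Section 6.2.3 also lists "follicle-stimulating hormone, human chorionic gonadotropin" within serum chemistry, which Table 13-1 schedules at Screening, Day 1, every week through Week 12 and at end of study. Further hCG values may therefore be obtained, but the Note does not require anyone to consult one before randomisation.

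6. **What is unaffected?** Both tests remain mandatory. A positive result excludes unless the investigator both suspects a false positive and chooses to enrol. Women of childbearing potential must still agree to contraception.

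**The case against.** The strongest case on the other side has five parts.

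- **The criterion still works.** A reader might infer that the Note stops criterion 10 from screening out pregnancy. The documents do not support that: testing is compulsory, a negative result is the default requirement, and the exception needs both suspicion and an active decision. This part stands and limits the point to the exception itself.

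- **There is no deviation and no problem for the per-protocol set.** Section 4.1 says "Deviations from the inclusion and exclusion criteria are not allowed because" they could compromise the study, and Section 7.5 ties the per-protocol set to meeting all inclusion criteria. A reader might infer that a woman admitted under the Note has an ambiguous status. She does not. The Note is printed inside criterion 10, so she meets the criterion as specified, just as a subject admitted under the criterion 13 exception does. This part stands too.

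- **The breadth was chosen.** The change statement in Amendment 1 also speaks of female subjects generally, so the current text matches the log. That is correct, and no mismatch between log and text is alleged. The rationale is used only as the sponsor's own reason for wording still in force, and that reason does not extend to premenopausal women.

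- **hCG is measured repeatedly anyway.** If the serum chemistry listing means a separate hCG at each draw, repeat values exist, although a central-laboratory result from Day 1 may arrive after the first dose. If it refers to the Screening pregnancy test itself, there is no independent confirmation before entry. The documents do not settle which. It would be wrong to say that no repeat hCG is collected, and equally wrong to treat the panel as a safeguard, because the Note does not refer to it.

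- **The group is tiny.** Entry is at age 50 or older, and harm further requires a true pregnancy misjudged as a false positive. This stands as a limit on size. It does not remove the inconsistency.

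**Conclusion.** The point holds in a limited form. As written, the Note and footnote i make the negative-test requirement overridable on investigator suspicion and discretion alone, for any woman, including women of childbearing potential. That is wider than the stated reason for the Note and less demanding than the standard applied to a positive drug test in the same section. Followed to the letter, it permits a pregnant woman to be randomised with no recorded basis.

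The size is small in numbers. The plan is for about 35 subjects, all aged 50 or older, and the documents do not say how many would be women of childbearing potential, so no frequency is offered. The per-protocol set definition, sample size, significance level and efficacy analysis are not affected. The case for acting is that the event, though rare, is potentially serious and the correction is slight.

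The conclusion rests on reading the Note as printed. It would weaken if site instructions outside these documents already required evidence and a record.

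**What to change.** Reconcile three texts with the stated reason for the exception: criterion 10, its Note in Section 4.1.1, and footnote i of Table 13-1. The women the exception covers should be the women it was written for.

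Apply to it the standard the protocol already uses in criterion 13: medical evidence supporting the exception, and the decision documented in the source documents and eCRF, in place before randomisation.

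The sponsor should set the exact clinical wording. In doing so it should check the wording against every branch of the postmenopausal definition and against surgically sterilised women. A rule built on amenorrhoea and follicle-stimulating hormone alone could shut out women on the hormone-replacement branch or after surgery, who are not the group at issue.

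The cost is a wording change in two places and, for a rare subject, a short delay to randomisation while the supporting evidence is assembled. No assessment, sample size or analysis needs to change.
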